10.1.1 Serious adverse event (SAE)

This study will use the FDA definition of SAE:

- Death
- Hospitalization or prolongation of hospitalization, or emergency room visits
- Persistent or significant disability or incapacity
- Suicide plans or attempts

10.2 CLASSIFICATION

All AEs will be classified according to severity and attribution.

10.2.1 Severity

- (0) No adverse event or within normal limits
- (1) Mild adverse event did not require treatment
- (2) Moderate adverse event resolved with treatment
- (3) Severe adverse event resulted in inability to carry on normal activities *and* required professional medical attention
- (4) Life threatening or disabling adverse event
- (5) Fatal adverse event

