treatment (Re-Timer) for people with probable PTSD led to clinical improvements in PTSD symptoms. While bright light is associated with some side effects (headache, eyestrain, nausea, agitation [45]), these often spontaneously remit [45, 46], and patients rarely discontinue due to side effects [46]. Bright light devices (with UV filter) are considered safe with no changes in ophthalmologic exams observed after 6 years of daily use (in fall and winter months) [47].

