8 END-OF-INTERVENTION/END-OF-STUDY

8.1 DISCONTINUATION OF INTERVENTION

Use of the Re-Timer will be stopped in the event of:

- Significant clinical deterioration or expressed suicidal ideation at the determination of the study team
- Severe treatment side effects at the determination of the study team
- Significant decline in physical health making compliance with the intervention either ill-advised or challenging to complete
- Participant request to discontinue therapy

Reasons for discontinuation will be documented, and all outcome assessments will proceed as scheduled, if possible.

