10.3 REPORTING

All SAEs will be reported by the PI to the safety monitor, IRBMED, NIMH, and FDA as appropriate within 5 days of the study team becoming aware of an event. Any initial SAE report will be followed by submission of a completed resolution report. In addition, the PIs will prepare an annual report on data collection and occurrence of any adverse events for review by the above-listed groups.

In the event that a patient withdraws from the study or the investigators decide to discontinue a patient due to SAE, the patient will be monitored by the PIs via ongoing status assessment until:

- A resolution is reached (i.e., the problem has resolved or stabilized with no further changes expected)
- The SAE is determined to be clearly unrelated to the study intervention, or
- The SAE results in death

Should a large number of unexpected SAEs occur, we will modify or terminate the trial if the events are severe. We will also monitor safety alerts, defined as events that are relevant to the study populations and pose safety risks to study participants. Examples of safety alerts would include a clinically significant increase in participant depression or anxiety or certain responses on the SAFTEE. Both SAEs and safety alerts will be tracked using a standardized form recording the date of the event, type of event, attribution of the event (e.g., judgment regarding whether it was intervention related), whether the event was resolved or controlled, and the resolution date.

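### AE severity grades 1 and 2 (10.2.1) rest on treatment and outcome, leaving some events with no grade, some with two, and some ranked in the wrong order

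*Combined protocol and SAP*

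**What the plan says.** Section 10.2 makes grading universal: "All AEs will be classified according to severity and attribution". Section 10.2.1 then gives a scale from 0 to 5. The three grades at issue are:

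- Grade 1: "1) Mild adverse event did not require treatment".
- Grade 2: "2) Moderate adverse event resolved with treatment".
- Grade 3: "3) Severe adverse event resulted in inability to carry on normal activities", joined by an emphasised 'and' to a second condition, that the event "required professional medical attention".

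Grade 4 covers life-threatening or disabling events and grade 5 fatal ones, with no condition on treatment or resolution. Nothing says what to do when an event meets no grade, or more than one.

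Section 10.4 gives the MPIs the task of evaluating, grading and reporting AEs. Section 10.3 provides for an annual report covering adverse events to the safety monitor, IRBMED, NIMH and, as appropriate, FDA. It adds that if many unexpected SAEs occur, "we will modify or terminate the trial if the events are severe". The SAE definition in 10.1.1 is separate and includes emergency room visits. The tracking form in 10.3 records resolution as its own item, but only for SAEs and safety alerts.

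**The concern.** A severity scale should order events by how bad they were. Here, apart from the labels, grade 1 depends on whether treatment was needed and grade 2 on whether treatment worked. Only grade 3 looks at function, and it adds a second requirement. The categories are therefore neither exhaustive nor mutually exclusive, and their order need not follow severity.

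This bears on the events the protocol expects. Section 2.1 names headache, eyestrain, nausea and agitation as the side effects of light and says "these often spontaneously remit [45, 46], and patients rarely discontinue due to side effects". Events that pass without treatment match the grade 1 wording, whatever their effect on the participant's day, unless they are disabling.

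At stake is the AE record that goes to the safety monitor and the oversight bodies. Two staff members grading the same event could defensibly choose different grades, or find none. The grade is also the only definition of 'severe' in the document when 10.3 asks whether unexpected SAEs are severe.

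**Working it through.** No sample-size or error-rate figure is involved, so the check is to apply the wording of 10.2.1 to each kind of non-fatal, non-life-threatening event.

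Inputs, all from 10.2.1: grade 1 = treatment not required; grade 2 = treated and resolved; grade 3 = normal activities lost and professional attention required; grade 4 = disabling. The labels (mild, moderate, severe) are set aside, because they do not define the boundaries. An event needing no treatment is taken as not having required professional attention either. Because 'disabling' is undefined, each case is read twice: with an event that stops normal activities not counted as disabling, and with it counted.

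| Event | Grades met, not counted as disabling | Grades met, counted as disabling |
|---|---|---|
| A. Activities kept; no treatment required | 1 | 1 |
| B. Activities kept; treated, resolved | 2 | 2 |
| C. Activities kept; treated, ongoing | none | none |
| D. Activities kept; treatment required, not given | none | none |
| E. Activities lost; no treatment required | 1 | 1 and 4 |
| F. Activities lost; treated, resolved, no professional attention required | 2 | 2 and 4 |
| G. Activities lost; treated, ongoing, no professional attention required | none | 4 |
| H. Activities lost; treated, ongoing, professional attention required | 3 | 3 and 4 |
| I. Activities lost; treated, resolved, professional attention required | 2 and 3 | 2, 3 and 4 |
| J. Activities lost; treatment required, not given | 3 if professional attention required, otherwise none | 4, plus 3 if professional attention required |

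Three results follow.

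1. **No grade.** Row C has no grade on either reading. An example is a headache treated at home and still present at the last visit, with the participant functioning normally. Row D is also ungraded. Rows G and J show that whether some incapacitating events have a grade depends on the undefined word 'disabling'.
2. **Wrong order.** On the first reading, row E is grade 1 and row B is grade 2. A participant kept from normal activities by agitation that needed no treatment is graded below one whose slight headache cleared after a remedy. On the second reading row E meets grades 1 and 4, which is no clearer.
3. **Two grades.** Row I meets grades 2 and 3 on both readings, with no rule for choosing between them.

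The gap can reach serious events. An emergency room visit is an SAE under 10.1.1. If the event was treated, is unresolved, and is judged neither to have stopped normal activities nor to be life threatening or disabling, it falls in row C: an SAE with no grade, when 10.3 asks whether the SAEs are severe.

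**The case against.** The strongest reply is that the scale is better than this suggests and that little depends on it. Much of that reply stands.

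- Grade 3 has a functional criterion and says nothing of resolution, so a reader should not infer that grades 1 to 3 all ignore severity.
- Grade 1 turns on whether treatment was required, not on whether it was given. An incapacitating event that went untreated although it needed care is not mild (row J).
- A treated, unresolved event is not always ungraded: it is grade 3 if incapacitating and needing professional attention (row H).
- A sensible assessor would give weight to the label and hesitate to call an incapacitating event mild. That relies on the assessor overriding the stated criterion.

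A reader might also infer that the rule for stopping the device is compromised. Section 8.1 does not support this. Its ground is "Severe treatment side effects at the determination of the study team", which rests on judgement and does not cite the grade. Nor does it follow that tolerability cannot be compared between 15, 30 and 60 minutes: weekly SAFTEE scores (9.10.1) are collected independently of the AE grade and can be compared by arm. Escalation for individual participants runs on SAFTEE, C-SSRS and symptom-worsening flags (9.10 and 12.3.1), and no analysis in Section 11 uses the grade.

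Finally, Section 10 names a separate Data and Safety Monitoring Plan as definitive. It is not among the documents reviewed and may define grading more fully.

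These points limit the consequence. They do not remove the gap in row C, the inversion between rows E and B, or the overlap in row I.

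**Conclusion.** The point holds in limited form. As written, 10.2.1 cannot do what 10.2 requires: it leaves a treated, ongoing, non-incapacitating event ungraded, puts a non-disabling event that stops activities but needed no treatment under the mild wording alone, and gives one class of event two grades. The first and third results hold on either reading of 'disabling'. The second holds where the event is not counted as disabling; where it is, the event meets grades 1 and 4 together.

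The effect falls on AE grading and safety reporting under 10.2 to 10.4, including the judgement of whether unexpected SAEs are severe. It does not reach the primary analysis, the 8.1 criterion, or a SAFTEE-based comparison of tolerability by arm. With no event frequencies in the documents, its size in participants cannot be given.

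The conclusion rests on a literal reading of 10.2.1 and on the Data and Safety Monitoring Plan not replacing this scale. If that plan holds a different scale, the two documents disagree and need reconciling; if it repeats this one, the defect stands. The change is worth making because it is cheap and the fault is on the face of the text.

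**What to change.** Redefine grades 1 to 3 in 10.2.1 by interference with normal activities, whether or not the event was treated: mild for none, moderate for some, severe where the event prevents them. Keep grades 4 and 5, and state that the highest grade met is assigned. Record treatment given and outcome (resolved or ongoing) as separate fields for all AEs, extending what 10.3 already does with resolution for SAEs and safety alerts. Under this rule row C takes grade 1 or 2 by interference, and rows E and I become grade 3, or grade 4 if judged disabling.

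SAFTEE scores may inform the grade but should not set it: they measure how bothered the participant was, which is not interference, and they do not cover events outside that instrument. Regrade events already recorded, and reconcile the scale with the Data and Safety Monitoring Plan.

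A smaller edit, adding ongoing events to grade 2 plus a tie-break rule, would close row C and settle row I but leave the inversion between rows E and B.

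The cost is one protocol paragraph, two form fields and a little regrading. The downside is that some events may move to a higher grade, so the AE table may look slightly less favourable.

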10.2.2 Attribution

- Definite: The AE is clearly related to the investigational agent(s)
- Probable: The AE is likely related to the investigational agent(s)

- Possible: The AE may be related to the investigational agent(s)
- Unlikely: The AE is doubtfully related to investigational agent(s)
- Unrelated: The AE is clearly not related to investigational agents(s)

10.3 REPORTING

All SAEs will be reported by the PI to the safety monitor, IRBMED, NIMH, and FDA as appropriate within 5 days of the study team becoming aware of an event. Any initial SAE report will be followed by submission of a completed resolution report. In addition, the PIs will prepare an annual report on data collection and occurrence of any adverse events for review by the above-listed groups.

In the event that a patient withdraws from the study or the investigators decide to discontinue a patient due to SAE, the patient will be monitored by the PIs via ongoing status assessment until:

- A resolution is reached (i.e., the problem has resolved or stabilized with no further changes expected)
- The SAE is determined to be clearly unrelated to the study intervention, or
- The SAE results in death

Should a large number of unexpected SAEs occur, we will modify or terminate the trial if the events are severe. We will also monitor safety alerts, defined as events that are relevant to the study populations and pose safety risks to study participants. Examples of safety alerts would include a clinically significant increase in participant depression or anxiety or certain responses on the SAFTEE. Both SAEs and safety alerts will be tracked using a standardized form recording the date of the event, type of event, attribution of the event (e.g., judgment regarding whether it was intervention related), whether the event was resolved or controlled, and the resolution date.

10.4 UNANTICIPATED PROBLEMS

Unanticipated problems, in general, will include any incident, experience, or outcome that meets ALL of the following 3 criteria:

- It is unexpected (in terms of nature, severity, or frequency) given (a) the research procedures that are described in the protocol-related documents, such as the IRB-approved research protocol, informed consent document, or other research materials; and (b) the characteristics of the subject population being studied.
- It is related or possibly related to participation in the research (possibly related means there is a reasonable possibility that the incident, experience, or outcome may have been caused by the procedures involved in the research).
- It suggests that the research places subjects or others at a risk of unknown harm or addition/increased frequency of harms (including physical, psychological, economic, legal, or social harm) than was previously known or recognized.

The MPIs will have ultimate responsibility for event reporting. Monitoring will occur by the research team who will then bring all AEs and UaPs to the attention of the MPIs for evaluation, gradation, and

appropriate reporting. The MPIs and the study coordinator will be responsible for overseeing data integrity, safety monitoring, and reporting of adverse events.

11 STATISTICAL CONSIDERATIONS

11.1 GENERAL APPROACH

The objective of this study is to establish a signification dose response relationship between the duration of morning light treatment and reduction in amygdala reactivity from baseline to treatment week 2 (study week 3) and/or treatment week 4 (study week 5).

Statistical analyses will include intent-to-treat and completer analysis. Data will be analyzed using responses at all three times (baseline, 2 [when data available] and 4 weeks) as dependent variables using a mixed-effects longitudinal model [106, 107] with participants as random intercepts to account for between participant variability and time as a predictor.

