		6.4.5	Added section on Pre-screening via REDCap & telephon										
		0.4.5	surveys, and the emailing of materials to prospective participants										
		6.5	Clarified that travel stipends are only available for visits to the research clinic/Rachel Upjohn building										
			Added beta blockers and opioids and SNRIs to the list of										
		7.5/7.6	contraindicated meds										
			Added Beck Scale for Suicidal Ideation										
			Added Demographics form, Work & Social Adjustment										
		9.5/9.6	Form, fMRI screening form, and Treatment Expectation										
		,	and Satisfaction forms; Insomnia Severity Index;										
			Morningness/Eveningness Questionnaire										
		9.71	Added section on fMRI practice										
		9.7.4	Added section on Emotional Regulation Task										
			Clarified screening process for fMRI as relates to										
		9.9.1	pregnancy and drug screening										
		12.2.2/12.3.3.1	Indicated that video files will be stored on MBox										
		12.3.2	Added section naming the Independent Safety Monitor										
		12.4	Added ERT and WSAS to abbreviations list										
		13	Added references for BSSI and WSAS questionnaire										
			Added footnote to SOA and language to section 5.1 that										
1 42		1.3; 5.1	allows for Visit 2 activities to occur on two separate days.										
Jan. 13,	3.0		Updated incentive schedule to reflect possibility of										
2020		6.5	receiving an additional travel stipend related to visit 2										
			schedule										
Feb. 4,	4.0	6.2	Updated Exclusion Criteria to specify excluding for										
2020	4.0	0.2	significant light treatment use and/or use in the past year										

5.0	6.4.3; 6.4.4	Updated recruitment strategies to specify flyering at the VA and removed flyering at the VA as a future									
		recruitment strategy.									
		Updated SOA to indicate that the PCL-5 and DASS will									
6.0	1.3	also be collected at lab visits 4 and 6; updated Table of									
		Contents									
7.0	3.1.5.1	Removed language that indicated only the clinician would be filmed.									
7.0	6.5	Outlined additional travel stipend amount depending on									
	0.5	distance which participant will be traveling to the lab.									
8.0	6.4.3	Updated to reflect that IRB approved study fliers will be									
10, 2020		posted on Wayne State University campus.									
October 9.0 13, 2020		Added drug test to lab visit 2									
		ALL LD . D: ./FMFDCF									

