1.3 SCHEDULE OF ACTIVITIES

Study Phase	Screening & Baseline 5																					I	nterv	entio	n												
Day Number 1							6	10	11	12	13	14	15	16	17	18	19	20	21	22	23	24	25	26	27	28	29	30	31	32	33	34	35	36			
Visit Number	٧1	v2 ⁶							٧3							٧4							٧5							9^							٧٧
Informed consent	Х																																				
Eligibility Confirmation	Х	х																																			
Vision Testing	Х																																				
Psychological assessment		Х																																			
Accelerometry		Χ	Χ	Χ	Х	Х	Х	Х	Х	Χ	Χ	Х	Х	Χ	Х	Х	Х	Х	Χ	Χ	Χ	Х	Х	Χ	Χ	Χ	Χ	Χ	Х	Х	Χ	Χ	Χ	Χ	Χ	Х	Χ
PSQI									Х														Х														Χ
Daily log ²		Х	Х	Х	Х	Х	Х	Х	Х	Χ	Х	Х	Х	Х	Х	Х	Х	Х	Х	Χ	Χ	Х	Х	Х	Χ	Χ	Χ	Χ	Х	Х	Χ	Χ	Χ	Х	Х	Х	Χ
Urine screen ³	Х	х							Х														Х														Χ
Breathalyzer	Х	Х							Х							Х							Х							Х							Χ
Clinician-administered assessments									х														Х														Х
Self-report questionnaires									Х							X ⁷							Х							X ⁷							Х
fMRI ⁴									Х																												Χ
Randomization									Х																												
Treatment expectation									Х																												
Light therapy										Χ	Х	Х	Х	Х	Х	Х	Х	Х	Х	Х	Х	Х	Х	Х	Х	Χ	Х	Χ	Х	Х	Χ	Χ	Х	Х	Х	Х	Х
Treatment fidelity – daily contact										Х	Х	х	х	Х	х	Х	х	х	Х	Х	Х	Х	Х	Х	Х	Х	Х	Х	х	х	Х	Х	Х	Х	Х	Х	Х
Treatment fidelity – data download & feedback																х							х							х							Х
AE Assessment (SAFTEE/CSSRS)	х	х							Х							Х							Х							Х							Х
Treatment satisfaction																																					Χ

^{1 –} Exact day number can vary by up to one week; 2 – Daily log will capture information about sleep time, treatment time, medication use, etc.; 3 – Urine drug screen administered via dipstick by study team at baseline and urine pregnancy screen to ensure drug free participants; 4 – fMRI must occur within 7 days of clinician-administered assessments; 5 – Final screening and eligibility confirmation occur on day 0/v1 and the start of the weeklong baseline period begins at v2; 6 – Visit 2 activities may be split across 2 days separated by no more than 1 month; 7 – Only the PCL-5 and DASS will be administered at these visits

2 Introduction

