5 STUDY DESIGN

5.1 OVERALL DESIGN

- Single-blinded randomized controlled mechanistic trial
- Parallel groups
- 3 study arms based on light treatment duration: 15-minutes, 30-minutes or 60-minutes/day
- 4-weeks of morning bright light treatment delivered via Re-Timer device

This is a 5-week study (1-week of baseline and 4-weeks of intervention) that includes a screening visit plus 6 additional study visits to evaluate outcomes and monitor progress. Potential participants are prescreened for major exclusion criteria using a combination of online and telephone surveys. On Day 0 (Visit 1) individuals are consented and eligibility confirmed using several self-report questionnaires. Final eligibility is confirmed after the clinician interviews on visit 2 do not reveal any exclusionary psychiatric conditions (see below).

Participants return to the lab for study visit 2 for a battery of psychological assessments to characterize the sample, and to begin the week-long baseline period (see Section 1.3 - Schedule of Activities). At this visit, participants are provided with their study materials (Actiwatch Spectrum, daily log, instructions to sleep according to a normal schedule, etc.). To minimize burden participant burden and to accommodate calendar challenges (e.g. time change), the activities for this visit may be split across 2 days such that the psychological assessments are done on one day and the distribution and training of study materials occur on a second day within 1 months' time.

On Day 8 (Visit 3) participants return to the lab for randomization and baseline outcome assessments. Morning light treatment begins on the morning of Day 9. Thereafter, participants come to the research lab weekly to assess adherence to the study procedures and intervention, and monitor for side effects. Outcome assessments occur on Day 8, Day 22 (week 2 of intervention) and Day 36 (week 4 of intervention). The exact day number of study visits and activities can vary by up to a week; and we will try to schedule study visits for the same time of day. While the plan is to schedule the fMRI for the same day as the psychological assessments, we do allow for a 7-day window in cases where same-day scheduling is not possible.

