11.3.2 Traumatic stress symptoms

We will also examine the clinician-administered (PSSI-5, HAM-D, HAM-A) and self-report measures (DASS, PCL-5) of traumatic stress symptoms with a mixed-effects longitudinal regression model as described above.

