11.3.3 Baseline Analysis and Covariate Adjustment

With minimization randomization, we do not expect groups differences in the distributions of potentially prognostic baseline variables. We will check for imbalances in other baseline variables not used in minimization including childhood trauma and objective measures of total sleep time (sleep duration), wake after sleep onset (sleep continuity) and sleep quality (PSQI) assessed prior to baseline and include them as covariates in the analyses as needed. To explore how much of the change in amygdala reactivity and traumatic symptom reductions are associated with an improvement in sleep, we will also include separately each potential intermediate outcomes of the weekly average of total sleep time, wake after sleep onset and sleep quality assessed prior to each study visit (Days 22, 36) as predictors of outcomes. We will also explore if diagnostic status (baseline SCID) moderates the treatment response.

12 Supporting Documentation & Oversight Considerations

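### By cross-reference, the exploratory symptom model covers only baseline, week 2 and week 4, so the PCL-5 and DASS scores scheduled at Visits 4 and 6 have no place in it

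*Combined protocol and SAP*

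**What the plan says.** **Collection.** The self-report row of the Schedule of Activities (Section 1.3) is marked at Visits 3, 4, 5, 6 and 7. For Visits 4 and 6, footnote 7 says: "Only the PCL-5 and DASS will be administered at these visits". The version history agrees, recording for version 6.0 that these two scales will "also be collected at lab visits 4 and 6". Visit 3 is the baseline outcome visit and the later visits are weekly, so each scale has five scheduled occasions: weeks 0, 1, 2, 3 and 4.

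**Analysis.** Section 11.1 specifies a mixed-effects model with a random intercept per participant and time as a predictor: "Data will be analyzed using responses at all three times (baseline, 2 [when data available] and 4 weeks) as dependent variables". Section 11.3.2, under Exploratory Analyses, covers the clinician-rated scales and the "self-report measures (DASS, PCL-5) of traumatic stress symptoms with a mixed-effects longitudinal regression model as described above". It lists no occasions of its own.

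**Related text.** Section 5.1 places outcome assessments on Days 8, 22 and 36 only. Section 11.3.3 uses weekly sleep averages "assessed prior to each study visit (Days 22, 36) as predictors of outcomes". Section 11 nowhere mentions week 1, week 3, Visit 4 or Visit 6.

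**The concern.** Collection of the two scales covers five occasions, while the analysis section still describes three. An analyst who follows Section 11.3.2 back to Section 11.1 fits weeks 0, 2 and 4 and sets the other scores aside.

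Two things are then given up. One is some precision in the dose-by-time estimate for the PCL-5 and DASS. The other is information from early leavers: a participant who attends Visit 4 and is lost before Visit 5 has post-light scores on both scales but contributes only a baseline value. That fits poorly with the intent-to-treat analysis in Section 11.1 and with Section 8.2, which keeps data from withdrawals so as to limit data loss.

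Leaving the occasions to inference also allows the choice between a three-visit and a five-visit model to be made after the results are seen.

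**Working it through.** The plan gives no power or precision figure for the symptom analysis, so there is none to reproduce. The checks below size the omission.

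**Inputs from the documents.** Planned enrolment 66 (Section 6); three model occasions (Section 11.1); five collection occasions for the PCL-5 and DASS (Section 1.3); random intercept per participant (Section 11.1); coding of dose and time to be settled after graphical review, with categorical time allowed (Section 11.2).

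**Assumptions.** Equal arms, the correlation values shown, and the dropout shares in step 4. The documents give none of these.

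**1. Scores without a stated use, per instrument**
- Scheduled: 66 × 5 = 330
- In the three-occasion model: 66 × 3 = 198
- Remainder: 330 − 198 = 132, and 132/330 = 40%

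**2. Linear time, random intercept, complete data**

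Variance of the dose-by-time slope = σ²(within) / [Σ(d − d̄)² × Σ(t − t̄)²]. The dose term and σ² are the same in both designs, so only the time term matters.
- Weeks 0, 2, 4: 4 + 0 + 4 = 8
- Weeks 0, 1, 2, 3, 4: 4 + 1 + 0 + 1 + 4 = 10
- Variance ratio, five visits to three: 8/10 = 0.80, a 20% cut
- Standard error ratio: √0.80 = 0.894, which is 10.6% smaller

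The ratio does not depend on the intraclass correlation. A generalised least squares calculation with 22 per arm gave 0.894 at correlations of 0.3, 0.5 and 0.7.

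**3. Linear time, correlation that decays**

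Take V(i,j) = (1 − n) × ρ^|t(i) − t(j)|, plus n on the diagonal, where ρ is the weekly correlation and n the share of variance that is independent noise. The slope variance is the time element of (X′V⁻¹X)⁻¹. Five-to-three variance ratios:

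| Weekly ρ | n = 0 | n = 20% | n = 30% |
|---|---|---|---|
| 0.3 | 0.943 | 0.919 | 0.905 |
| 0.5 | 0.985 | 0.956 | 0.939 |
| 0.7 | 0.998 | 0.967 | 0.946 |
| 0.9 | 1.000 | 0.936 | 0.906 |
| 0.95 | 1.000 | 0.901 | 0.872 |

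The cut is therefore about 0 to 13% over this range. A larger noise share moves it towards the 20% of step 2.

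**4. Categorical time, dose effect on change from baseline to week 4**
- Complete data: variance ratio 1.00. The two extra visits add nothing to this contrast.
- With dropout: assume a share p of participants is lost between Visits 4 and 5, and the same share between Visits 6 and 7.

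| p at each point | Constant correlation 0.5 | Constant correlation 0.7 | ρ = 0.9, n = 20% |
|---|---|---|---|
| 5% | 0.992 | 0.988 | 0.989 |
| 10% | 0.984 | 0.976 | 0.976 |
| 15% | 0.976 | 0.963 | 0.962 |

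The cut is about 1 to 4%.

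**The case against.** **The three occasions may be imaging times.** The Section 11.1 sentence follows the amygdala objective, and its bracket about availability at week 2 fits the dropped Visit 5 scan, not the questionnaires, which remain scheduled at Visit 5. The cross-reference in Section 11.3.2 could then carry over only the type of model. This stands in part. A reader might infer that the plan expressly excludes the Visit 4 and 6 scores; it does not, and the omission arises only by cross-reference. But no text adds weeks 1 and 3, and Section 5.1 independently limits outcome assessments to Days 8, 22 and 36. Even on the looser reading, the occasions would be unspecified and the same sentence would be needed.

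**The scores may serve monitoring.** Section 3.1.2 has anxiety and depression measures completed throughout the study, and Section 12.3.1 flags worsening of more than 25%. The DASS could feed that review. This is plausible, but Section 12.3.1 names neither instruments nor visits, the PCL-5 is a PTSD scale, and use for monitoring would not prevent analysis.

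**Common occasions keep the five scales comparable.** This is a defensible choice, but the plan does not state it as one.

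**The gain is small.** This stands. A reader might infer that a fifth of the precision is lost in general; that figure needs linear time and constant correlation. Section 11.2 fixes neither the coding of time nor a linear trend, and the study's stated interest is change to week 2 and/or week 4.

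**Conclusion.** The point holds as a minor improvement. Followed as written, Sections 11.1 and 11.3.2 give no place to 40% of the scheduled PCL-5 and DASS scores.

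The 20% cut in slope variance applies to the random-intercept model with linear time and complete data. The 0 to 13% range rests on assumed weekly correlations of 0.3 to 0.95 and noise shares up to 30%. The 1 to 4% gain in the categorical week 4 contrast rests on the assumed dropout.

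A reader might also infer that the trial's main result is weakened. The documents do not support that. The hypothesis and go/no-go criterion concern amygdala reactivity only, no scan takes place at Visits 4 or 6, and the symptom analysis is labelled exploratory.

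**What to change.** In Section 11.3.2, state that the PCL-5 and DASS are modelled at weeks 0, 1, 2, 3 and 4, and the PSSI-5, HAM-D and HAM-A at weeks 0, 2 and 4. State in the same place whether time is linear or categorical for these models. If the sponsor intends the Visit 4 and 6 scores for monitoring only, saying so would remove the ambiguity but forgo the gain.

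The cost is a sentence or two in the analysis section, with no new data, visits or participant burden. It should be settled before outcome data by arm are examined.
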